 **Foundations**

What Works Centre for Children & Families

foundations.org.uk

Pilot RCT of Let's Connect - Fostering Communities

Intervention developer	The Copeland Center and Barnardo's
Delivery organisations	Barnardo's
Evaluator	Coram
Principal Investigator	[name], Head of Impact and Evaluation, Coram
Protocol author(s)	[name], [name], [name], [name], [name], [name] and [name]
Type of trial	Pilot randomised controlled trial (RCT) with 50:50 randomisation at family level to two arms: intervention and control
Age or status of participants	Foster families (foster children, foster carers, and birth children of foster carers), kinship carers, and their birth and kinship children
Number of participating sites	3 local authorities – Hull City Council, North Lincolnshire Council, North East Lincolnshire Council
Number of children and families	Target for randomisation: 178 fostering households with 311 foster carers, 544 foster children, 25 other adults, 59 birth children (plus kinship households, numbers unknown)
Primary outcome	1. Foster/kinship carer wellbeing (Warwick Edinburgh Mental Wellbeing Scale)
Secondary outcome(s)	2. Foster/kinship carer perceived peer support (self-reported number of 'other local foster or kinship carers you could ask for help if you needed' (0+)) 3. Foster child, kinship child and birth child mental health and wellbeing (Brief Assessment Checklists for Children and Adolescents;

	Strengths and Difficulties Questionnaire – available for foster children only 4. Foster/kinship family relationships (SCORE-15) 5. Foster placement stability (number of placement changes)
Exploratory outcome(s)	6. Foster carer turnover 7. Mental health referrals (referral of foster/kinship children to CAMHS)
Contextual factors	Receipt of other mental health and emotional wellbeing support and services Extent of existing community connections and networks among foster and kinship families

Summary

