Is the intervention a good use of resources?	4. How much does it cost Barnardo's and local authorities to introduce WRAP in the first year?	Cost evaluation

⁴ Dependent on sample sizes, we may also be able to address generic questions 'Does the intervention work differently for some groups?' and 'Does the intervention work differently in some places?' with these quantitative outcome measures.

Impact evaluation

Specific evaluation questions

Our impact evaluation will seek to answer whether the intervention works through a series of primary, secondary and exploratory evaluation questions.

Primary outcome

1. What impact does referring a family to WRAP, relative to usual support for the mental health and wellbeing of fostering and kinship care families, have on **carers' wellbeing**?

Secondary outcomes

What impact does referring a family to WRAP, relative to usual support for the mental health and wellbeing of fostering and kinship care families, have on:

2. ...**carers' perceived peer support** as measured by the number of other foster or kinship carers a carer could ask for help if needed?
3. ...the **mental health of children** in fostering and kinship households, as reported by their carers?
4. ...**carers' family relationships**?
5. ...the rate of **placement changes**?

Exploratory outcomes

6. What impact does referring a family to WRAP, relative to usual support for the mental health and wellbeing of fostering and kinship care families, have on **carer turnover**?
7. What impact does referring a family to WRAP, relative to usual support for the mental health and wellbeing of fostering and kinship care families, have on whether **children are referred to Child and Adolescent Mental Health Services (CAMHS)**?

There may also be scope to answer two further questions through sub-group analysis, dependent on sample sizes: does the intervention work differently for some groups (e.g. kinship carers, foster carers, other adults etc.); and does the intervention work differently in some places? However, given the expected sample size, these issues will most likely be explored solely through the process evaluation.

Design Trial type and number of arms	Pilot randomised controlled trial (RCT) with 50:50 randomisation to two arms: intervention and control
Unit of randomisation	Family (fostering or kinship household)
Stratification variables (if applicable)	By local authority (Hull, North Lincolnshire, North East Lincolnshire)

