Primary outcome	Variable	1. Carer wellbeing
	Measure (instrument, scale)	1. Carer self-reported wellbeing using the Warwick Edinburgh Mental Wellbeing Scale (Tennant et al., 2007) within an online survey
Secondary outcome(s)	Variables	2. Perceived peer support 3. Mental health of children in fostering and kinship households 4. Family relationships 5. Placement stability
	Measure(s) (instrument, scale)	2. Self-reported number of other local carers a foster carer or kinship carer reports they are able to contact for help if needed (0+) (self-reported perceived peer support) asked within an online survey 3a. Carer-reported child wellbeing using the Brief Assessment Checklist for Children and Adolescents (20 item) (Tarren-Sweeney, 2013) in an online survey 3b. Foster child wellbeing using the Strengths and Difficulties Questionnaire total difficulties score (Goodman, 2001) from a local authority administrative data return 4. Carer self-reported family relationships using the SCORE-15 (15 item) (Stratton et al., 2010) in an online survey 5. Number of placements, dates of placement changes, reasons for placement changes (child-level) from a local authority administrative data return
Exploratory outcome(s)	Variables	6. Carer turnover 7. The rate of referrals of children to Child and Adolescent Mental Health Services (CAMHS)
	Measure(s) (instrument, scale)	6. Carer turnover, reason for carer ceasing to be a carer (carer level) 7. Whether a child has been referred to CAMHS between randomisation and end of reporting period

--	--	--

There are a number of outcome measures we could use. We have consulted our advisory committee (four foster carers, two academics and one Fostering Consultant) in finalising our choice of measures for primary data gathering directly from foster families. In line with WRAP’s emphasis on wellbeing, we selected the Warwick Edinburgh Mental Wellbeing Scale as our primary outcome measure .

After consulting with local authorities on our data request, we have selected variables that are accessible for local authorities. Referrals to CAMHS may prove challenging due to data availability but local authorities have until March 2024 to address any challenges with sharing this. It is reasonable to assume that placement changes and foster carer turnover are likely to be correlated with poor wellbeing (Rubin et al., 2007;⁵ Adams et al., 2018⁶).

Randomisation

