We can expect that some children and young people will move to a randomised household during the observation period of the study, and that a proportion of these will move to a household randomised to a different trial arm. The Children's Commissioner (2020) found that, among children in care on 31 March 2019, most children (68%) had remained in their placement throughout the previous year, but 32% experienced one or more placement moves, 10% had experienced two or more placement moves, and 4.1% had experienced three or more. Teenagers and older children had the highest rates of placement instability. We have planned our administrative data returns to capture child and family ID codes, in order to trace the movement of children between households. We will report on the proportion of children that move between randomised households, in order to estimate the degree of trial arm 'contamination' in the current study and to predict this for a future full-scale RCT. We will also explore this in a compliance analysis (see Analysis plan).

Participants

The intervention and trial takes an inclusive approach to recruitment within households. The sample will therefore be made up of:

- Foster carers
- Kinship carers
- Foster children
- Kinship children
- Birth children, including children by blood, marriage, or legal adoption
- Other adults and children in fostering and kinship households, such as relatives and partners

Social workers also form part of fostering and kinship communities. Barnardo's will deliver services to FSWs as part of this programme, but social workers will not be randomised. Barnardo's have invited all FSWs in the three local authorities to take part in the WRAP intervention ahead of the trial, to aid programme buy-in and referrals.

Three local authorities volunteered to take part in the trial: Hull City Council; North East Lincolnshire Council; and North Lincolnshire Council.

Table 1. Information about participating local authorities

Local authority	Region	Type	Ofsted rating
Kingston Upon Hull City Council	Yorkshire and the Humber	Unitary	Requires improvement to be good (2023)
North East Lincolnshire Council	Yorkshire and the Humber	Unitary	Inadequate (2021)
North Lincolnshire Council	Yorkshire and the Humber	Unitary	Outstanding (2022)

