We will request administrative data from local authorities in March 2024. We will follow DfE SSDA903 requirements to the greatest extent possible, to minimise burden. Some data will have the foster child as the unit of analysis, and some will have the carer as the unit of analysis. We will use an Excel template for the data request that will be partially completed with demographic information about carers and children provided at randomisation. This entails routinely collected data on the care status and living arrangements of children, numbers and dates of placement changes, foster carer turnover management information (unique ID of the foster carer and step-down dates), and Strengths and Difficulties Questionnaire (SDQ) total difficulties scores for foster children (and date of the score and the unique ID of the child). We will gather SDQ scores from local authorities in March 2024, which according to published figures should be available for around 84% of looked-after children. A full breakdown of variables is provided in the spreadsheet template in Appendix 2.

For our secondary outcome of **placement changes**, we will seek data on the following variables for each foster child:

1. Number of placements since randomisation

¹⁷ Collins, J., Gibson, A., Parkin, S., Parkinson, R., Shave, D., & Dyer, C. (2012). Counselling in the workplace: How time-limited counselling can effect change in well-being. *Counselling and Psychotherapy Research*, 12(2), 84-92.

¹⁸ Maheswaran, H., Weich, S., Powell, J., & Stewart-Brown, S. (2012). Evaluating the responsiveness of the Warwick Edinburgh Mental Well-Being Scale (WEMWBS): Group and individual level analysis. *Health and Quality of Life Outcomes*, 10(1), 1-8.

¹⁹ Hamilton, E., Carr, A., Cahill, P., Cassells, C., & Hartnett, D. (2015). Psychometric properties and responsiveness to change of 15- and 28-item versions of the SCORE: A family assessment questionnaire. *Family process*, 54(3), 454-463.

2. Date of first placement change since randomisation (if applicable)
3. Nature of second placement (if applicable)
4. Reason for first placement change (if applicable)
5. Other reason for first placement change (if applicable)
6. Date of second placement change since randomisation (if applicable)
7. Nature of third placement (if applicable)
8. Reason for second placement change (if applicable)
9. Other reason for second placement change (if applicable)
10. Date of third placement change since randomisation (if applicable)

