- Date of first WRAP session attended
- Number of WRAP sessions attended
- Whether WRAP was received by other members of the household, which members
- Why WRAP did not take place ('refer for WRAP group') or why WRAP did take place ('do not refer' group)? (if applicable)
- SDQ score at randomisation [provided by Coram]
- Date of SDQ at randomisation [provided by Coram]
- Second SDQ score
- Date of second SDQ score
- Version used for second SDQ score
- Number of placements since randomisation (if applicable)
- Nature of second placement (if applicable)
- Reason for first placement change (if applicable)
- Date of second placement change since randomisation (if applicable)
- Nature of third placement change since randomisation (if applicable)
- Reason for second placement change (if applicable)
- Date of third placement change since randomisation (if applicable)
- Nature of fourth placement change since randomisation (if applicable)
- Reason for third placement change (if applicable)
- Referral(s) made to CAMHS since randomisation
- Date of referral(s) to CAMHS (if applicable)
- Reasons for referrals to CAMHS (presenting issues) (if applicable)
- Comments on data (optional)

Final data return – carer-level data:

- Local authority name [provided by Coram]
- Family ID [provided by Coram]
- Child ID [provided by Coram]
- Randomisation outcome 'refer for WRAP' (intervention) group or 'do not refer for WRAP (control) group [provided by Coram]
- Date of randomisation [provided by Coram]
- Number of foster/kinship children in household at randomisation [provided by Coram]
- Number of other (birth) children in household at randomisation [provided by Coram]
- Number of foster/kinship children currently in household
- Number of other (birth) children currently in household
- Reason for changes in number of children in household (if applicable)
- Did the carer receive WRAP?
- Date of first WRAP session attended
- Number of WRAP sessions attended
- Whether WRAP was received by other members of the household, which members

- Why WRAP did not take place (if in 'refer for WRAP group') or why did WRAP take place (if in 'do not refer')
- Has the foster carer ceased fostering? (yes/no/unknown)
- Plans to cease fostering in the next year? (yes/no/unknown)
- Reasons foster carer has ceased fostering/plans to (if applicable)
- Contributing factors
- Comments on data (optional)

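### The placement return asks for placements rather than changes, does not define the count for a child who never moves, and collects no reason beyond the third change

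*Protocol*

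**What the plan says.** The outcome is a count or rate of changes. The summary table at the front of the Protocol gives "Foster placement stability (number of placement changes", and the evaluation questions ask about "the rate of placement changes". The design table under Impact evaluation instead describes the measure as "Number of placements, dates of placement changes, reasons for placement changes (child-level) from a local authority administrative data return".

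The fields to be collected are listed twice.

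- Under Outcome measures, the count field is "Number of placements since randomisation". The list then has date, nature and reason fields, with a free-text other reason, for a first, second and third change. The placement that follows the first change is labelled "Nature of second placement (if applicable".
- In Annex 3 (final data return, child level), the count field is "Number of placements since randomisation (if applicable" and the last reason field is "Reason for third placement change (if applicable".

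The Data cleaning section sets out an anticipated rule that includes or excludes each change by its reason. Status-only changes, where the child stays with the same carer, are on the exclude side. They are nevertheless one of the reason categories that local authorities are asked to report.

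**The concern.** The outcome and its count field use different units, and no sentence links them. Three authorities will complete the return separately, so the same stable child could be entered in different ways, and a blank could mean either no move or not reported.

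The reason rule works change by change, but the return has room for only three reasons. Children with more changes than that are the ones about whom a stability outcome should be most informative. This is a data-capture problem: a later analysis plan can define how to handle the gap, but cannot recover a reason that was never requested.

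**Working it through.** The protocol gives no sample size or event count for this outcome, so there is no figure to reproduce. The check sets the fields against the rule and then sizes the gap.

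**1. What the count field can mean.** In the Outcome measures list the first change leads to the second placement, so the placement at randomisation is implicitly the first. That suggests changes = placements − 1. For a child who never moves:

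| Reading of the field | Entry |
|---|---|
| Placement at randomisation is counted | 1 |
| Only new placements are counted | 0 |
| Treated as not applicable | blank |

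**2. When the count field is needed.** Each of the first three changes has its own reason field. For a child with three or fewer changes, the analyst counts the eligible reasons and does not need the total.

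**3. Where the rule fails.** A fourth change has no reason field. Calling its reason unknown does not help, because the unknown-reason code is on neither the include nor the exclude side of the Data cleaning table. Slots can also be used up. If a child's sequence is status-only, move, status-only, move, the second real move is the fourth change and is lost to the rule.

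**4. How many children.** The Randomisation section cites one-year figures for children in care: 68% no move, 32% one or more, and "10% had experienced two or more placement moves, and 4.1% had experienced three or more".

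- Exactly one: 32 − 10 = 22%. Exactly two: 10 − 4.1 = 5.9%.
- Two or fewer: 68 + 22 + 5.9 = 95.9%.
- Four or more cannot exceed three or more, so at most 4.1% in a year. That is at most 0.041 × 544 = 22 of the 544 target foster children, and at most 4.1/32 = 13% of those who move.
- Extending the ratio 4.1/10 one step (assumption): 4.1% × 0.41 = 1.7%, about 9 children.
- Negative binomial fitted to the four cells (assumption): size r = 0.851, mean μ = 0.483. It returns 31.8%, 10.8% and 3.7% for one, two and three or more moves, against 32%, 10% and 4.1%. It puts 1.3% at four or more, about 7 children.
- The same model with μ scaled to 16 months (March 2023 to July 2024): μ = 0.483 × 16/12 = 0.644, giving 2.6% at four or more. That is about 14 children, or 2.6/38.1 = 7% of movers.
- A slightly different fit (r = 0.98, mean 0.47) gives 1.1% and 2.3%.

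The 4.1% ceiling is for one year and counts moves. It makes no allowance for status-only changes filling slots, for which the protocol gives no frequency.

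**5. The two field lists compared.** Annex 3 omits the date of the first change and the other-reason fields that the Outcome measures list contains. For a child with a single change, Annex 3 therefore collects no date. Annex 3 also asks for the nature of the second placement, but then for the nature of the third and fourth placement *change*, where the Outcome measures list has the third and fourth placement. So it names a fourth change without a date or reason field for it.

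**The case against.** The strongest reply is that this is loose labelling. The Outcome measures text says elsewhere that the request covers numbers and dates of placement changes, and the numbering points to placements − 1. Definitions may also sit in the Excel template or the guidance sent with it, and Annex 3 lists labels only. The reason rule is provisional, the outcome is secondary and the trial is a pilot. The one-year figures cover all children in care, whereas the trial excludes families on the verge of placement breakdown, and later-randomised families are followed for less time, so the affected share may be smaller still.

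Much of this stands, and it rules out three stronger inferences that a reader might draw.

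- *That the outcome count cannot be derived.* It can be, from the reason fields, for every child with three or fewer changes.
- *That every child becomes an event in the any-change logistic model.* That sensitivity analysis is defined on changes and needs no reason code. Scoring a placement count of 1 as a change would contradict its own wording.
- *That a treatment ratio would be pulled strongly towards 1.* This needs placements to be used uncorrected in a ratio model. No count model is specifically assigned to this outcome: Poisson and zero-inflated Poisson are conditional sensitivity tests, and the model list names the latter for peer support. In a linear model, adding 1 to every child leaves the treatment coefficient unchanged. The local-authority fixed effect would absorb a shift that is constant within an authority.

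The reply does not cover blanks, inconsistent entry within an authority, or the missing reasons beyond the third change. Any reason-based rule, provisional or final, meets that last limit.

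**Conclusion.** The point holds as a limited defect in data capture. The count field does not match the outcome and leaves the entry for a stable child undefined, although the numbering suggests placements − 1. The anticipated reason rule cannot be applied to a fourth or later change. On the cited one-year figures this touches at most 4.1% of children; the fitted distribution puts it at about 1% to 3% over 12 to 16 months. Those figures assume that the cited population resembles the trial's and that children's move rates persist over time, and they leave out slots taken by status-only changes. Few children are affected, but they are the least stable ones. The mismatch between Annex 3 and the Outcome measures list is a separate, plain inconsistency. The change is worth making because it is cheap and must come before the returns are collected.

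**What to change.** - Replace the count field in both lists with *number of placement changes since randomisation (enter 0 if none)*.
- Replace the three fixed slots with one row per change: date, reason code (with free text for other reasons) and nature of the new placement.
- State that the outcome is derived from those rows after the reason rule is applied, so that status-only changes are identified and no longer displace real moves.
- Align Annex 3 with the Outcome measures list: restore the date of the first change and the other-reason detail, and use placement and placement change consistently in the nature fields.

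The cost is an edit to the template and to the two field lists. The protocol already follows the SSDA903 requirements as far as possible and takes its reason codes from that return. The downside is a slightly longer return for the few children with four or more changes.
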